10.9.3 Data and Safety Monitoring Board (DSMB)

The DSMB is an independent multidisciplinary group restricted to individuals free of apparent significant conflicts of interest. The source of these conflicts may be financial, scientific, or regulatory in nature. The DSMB is typically composed of at least two physicians with experience relevant to the clinical investigation and a biostatistician.

The DSMB will serve in an advisory role to the Sponsor to ensure safety by reviewing cumulative data from the clinical investigation at prescribed intervals for safeguarding the interests of enrolled subjects and those patients yet to be enrolled, as well as the continuing validity and scientific merit of the clinical investigation. The composition, frequency of the meetings, and the statistical monitoring guidelines are described in detail in the DSMB charter.

The DSMB may consider a recommendation for modifications or termination of the clinical investigation based on any perceived safety concerns regardless of statistical significance. The recommendations of the DSMB are not binding, and all final decisions related to clinical investigations modifications rest with the Sponsor.

10.9.4 Clinical Events Committee (CEC)

The CEC is an independent adjudication body comprised of qualified physicians who are not participants in the clinical investigation. The CEC will review and adjudicate pre-specified events reported by investigators or identified by Safety personnel for the clinical investigation as defined in the CEC charter and according to definitions provided in this CIP.

11.0 DATA HANDLING AND RECORD KEEPING

Sponsor and/or its affiliates will maintain documentation of the systems and procedures used in data collection for the duration of the clinical investigation.

CRF data collection will be performed through a secure web portal and only authorized personnel will access the EDC system using a unique username and password to enter, review or correct data. Passwords and electronic signatures will be strictly confidential.

The data will be subjected to consistency and validation checks within the EDC system and supplemental review by the Sponsor.

At the end of the clinical investigation, completed CRF images with the date-and-time stamped electronic audit trail indicating the user, the data entered, and any reason for change (if applicable) will be provided to the investigational sites, if requested.

For the duration of the clinical investigation, the Investigator will maintain complete and accurate documentation including, but not limited to, medical records, clinical investigation progress records, laboratory reports, CRFs, signed ICFs, device accountability records (if applicable), correspondence with the IRB/EC and clinical investigation monitor/Sponsor, adverse event reports, and information regarding subject discontinuation or completion of the clinical investigation.

Clinical Investigation Plan for Europe

11.1 Protection of Personally Identifiable Information

The Sponsor respects and protects personally identifiable information collected or maintained for this clinical investigation.

The Sponsor implements technical and physical access controls to ensure that Personal Information is accessible only to and processed only on a 'need to know' basis, including periodic review of access rights, and revocation of access when an individual's employment is terminated or the individual transitions to a role that does not require access to Personal Information, and appropriate restrictions on physical access to premises, facilities, equipment, and records containing Personal Information.

The Sponsor requires the investigational sites to enter only pseudonymous Personal Information (key-coded) necessary to conduct the clinical investigation, such as the patient's medical condition, treatment, dates of treatment, etc., into Sponsor's data management systems. The Sponsor discloses as part of the clinical investigation informed consent process that some Sponsor representatives still may see Personal Information at the participating sites for technical support of the participating physicians on the device implant or procedures, monitoring and quality control purposes. All parties will observe confidentiality of Personal Information always throughout the clinical investigation. All reports and data publications will preserve the privacy of each subject and confidentiality of his/her information.

The Sponsor data management systems and processes were designed, developed, and tested according to industry standards to appropriately safeguard Confidential Information (including any Personal Information) against unauthorized access and/or interference by third parties, intrusion, theft, destruction, loss or alteration. Clinical Investigation data are encrypted in transit and at rest.

The Sponsor maintains a Privacy Incident procedure that complies in all respects with Applicable Law and industry best practices.

11.2 Data Management Plan

A Data Management Plan (DMP) will describe procedures used for data review, data cleaning, issuing and resolving data discrepancies, and database locking. If appropriate, the Sponsor may update the DMP throughout the duration of the clinical investigation. The Sponsor will track and document control all revisions.

11.3 Source Documentation

Regulations and GCP require the Investigator to maintain information in the subject's original medical records that corroborates data collected on the CRFs. To comply with these regulatory requirements/GCP, sites should include the following information in the subject record at a minimum and if applicable to the clinical investigation:

- Medical history/physical condition of the subject before involvement in the clinical investigation sufficient to verify CIP entry criteria

Clinical Investigation Plan for Europe

- Dated and signed notes on the day of entry into the clinical investigation referencing the Sponsor, CIP number, subject ID number, and a statement that informed consent was obtained
- Dated and signed notes from each subject visit (for specific results of procedures and exams)
- AEs reported and their resolution, including supporting documents, such as discharge summaries, catheterization laboratory reports, ECGs, and lab results including documentation of site awareness of SAEs and of investigator assessment of device relationship for SAEs.
- Subject's condition upon completion of or withdrawal from the clinical investigation
- Any other data required to substantiate data entered into the CRF
- Patient reported outcome measures may be completed using CRF worksheets. This serves as source documentation.

11.4 Case Report Form Completion

Site research personnel trained on the CIP and CRF completion will perform the primary data collection clearly and accurately based on source-documented hospital and/or clinic chart reviews. The investigator will ensure accuracy, completeness, legibility, and timeliness of the data reported to the Sponsor on the CRFs and in all required reports.

Sites will collect data on all subjects enrolled into the clinical investigation.

Only authorized site personnel will be permitted to enter the CRF data through the EDC system deployed by the Sponsor. The Sponsor will use an electronic audit trail to track any subsequent changes of the entered data.

11.5 Record Retention

The Sponsor and Investigator/Site will archive and retain all documents pertaining to the clinical investigation as per the applicable regulatory record retention requirements. The Investigator must obtain permission from Sponsor in writing before destroying or transferring control of any clinical investigation records.

11.6 Investigational Devices Accountability

The Sponsor ships investigational products only to the Principal Investigator (the responsible leader of the investigational site) or his/her legal designee of each site, after sites receive documentation of site activation and shipping authorization is complete.

The Investigator or an authorized designee must maintain adequate records of the receipt and disposition of each investigational device, including part number, batch/lot number, and serial number (if applicable), date used, subject identification, and treating physician.

Clinical Investigation Plan for Europe

Storage locations for the devices at investigational sites must be locked with access restricted only to investigators and authorized personnel.

Sites must return all investigational devices associated with a device failure or device deficiency immediately to the Sponsor.

The clinical investigation will use an Inventory (Device) Accountability Log supplied by the Sponsor for device accountability. The Inventory Accountability Log must document the disposition of all investigational devices including those that have been returned to Sponsor.

12.0 ETHICAL CONSIDERATION

12.1 Institutional Review Board/Medical Ethics Committee Review and Approval

The Principal Investigator at each investigational site will obtain IRB/EC approval for the CIP and ICF/other written information provided to the patient prior to consenting and enrolling patients in this clinical investigation. The site must receive the approval letter prior to the start of this clinical investigation and provide a copy to the Sponsor.

Sites will submit any amendments to the CIP as well as associated ICF changes to the IRB/EC and written approval obtained prior to implementation, according to each institution's IRB/EC requirements.

No changes will be made to the CIP or ICF or other written information provided to the patient without appropriate approvals, including IRB/EC, the Sponsor, and the regulatory agencies (if applicable).

Until the clinical investigation is completed, the Investigator will advise his/her IRB/EC of the progress of this clinical investigation, per IRB/EC requirements. Written approval must be obtained from the IRB/EC yearly to continue the clinical investigation, or according to each institution's IRB/EC requirements.

Sites will not perform any investigative procedures, other than those defined in this CIP, on the enrolled subjects without the written agreement of the IRB/EC and the Sponsor.

13.0 CLINICAL INVESTIGATION CONCLUSION

The study is complete when all active subjects across all active study sites have completed their 12-month follow up visits or the 12-month visit window has passed and approval for commercial use is received from local regulatory agencies. Site closure for enrolling centers will begin once the study is complete.

A final report will be generated and submitted to all sites, all competent authorities, and all IRBs/ECs within one year of study completion.

Clinical Investigation Plan for Europe

The clinical investigation will be closed when:

- All sites are closed AND
- The final report has been provided to investigators or the Sponsor has provided formal documentation of clinical investigation closure.

14.0 PUBLICATION POLICY

The data and results from the clinical investigation are the sole property of the Sponsor. The Sponsor shall have the right to access and use all data and results generated during the clinical investigation. Investigators will not use clinical investigation-related data without the written consent of the Sponsor for any purpose other than for clinical investigation completion or for generation of publication materials, as referenced in the Clinical Trial Agreement. Single-center results are not allowed to be published or presented before the multi-center results. The Sponsor must review and approve any proposals for publications or presentations by the investigators in a timely manner in compliance with the Sponsor's publication policy set forth in the Clinical Trial Agreement.

Upon receiving IDE approval from the FDA, the Sponsor will be responsible for registering this clinical investigation on ClinicalTrials.gov website, in accordance with the International Committee of Medical Journal Editors guidelines, or any other applicable guidelines. Sponsor shall be responsible for any such registration and results posting as required by the ClinicalTrials.gov website. Institution and/or Principal Investigator(s) shall not take any action to register the clinical investigation. A full report of the pre-specified outcomes, regardless of the results, will be made public through the ClinicalTrials.gov website no later than 12 months after clinical investigation completion, as required by section 801 of the FDA Amendments Act. If this clinical investigation is terminated early, the Sponsor will make every effort to hasten the release of the pre-specified outcomes through the ClinicalTrials.gov website.

15.0 RISK ANALYSIS

15.1 Anticipated Clinical Benefits

Implantation of the LP for cardiac pacing could offer certain advantages as compared to a transvenous pacemaker. Specifically, the benefits that are associated with the use of the LP could include:

- Percutaneous procedure with no incision or generator pocket needed;
- Eliminates the need for lead (no risk of lead fracture, lowers risk of infection);
- Eliminates the need for a pocket (no scar and/or evidence of the presence of a pacemaker);
- Eliminates the need for connectors (eliminates connector complications);
- Eliminates the visible scar at the pectoral implant site used for transvenous implants;

Clinical Investigation Plan for Europe

- May reduce the need for activity restrictions of the left upper extremity after transvenous pacemaker implantation;

15.2 Foreseeable Adverse Events and Anticipated Adverse Device Effects

Risks associated with the specified device and procedure, together with their likely incidence, are described in the IB. There may be risks related to the device under investigation that are unknown at present. Likewise, the exact frequency of the risk may be unknown. A list of foreseeable adverse events and anticipated adverse device effects can be found in Appendix IV.

15.3 Residual Risks Associated with the Device Under Investigation, as Identified in the Risk Management Report / Risk Analysis Report

Risk analysis of the Aveir DR LP system has been performed in accordance with the Risk Analysis Plan, Failure Mode Effect Analysis), and Hazard Analysis to systemically identify potential hazards associated with the design and use of this device. Based upon bench testing and prior Abbott sponsored clinical study data, all risks have been identified and mitigated as far as possible through application of appropriate controls and inspections and determined to be within acceptable levels.

Residual risks are likewise disclosed in the IFU in the form of clear instructions of what actions to take or to avoid, to avoid a hazardous situation of harm from occurring (contra-indications, warnings, and precautions). The anticipated AEs disclosed in the IFU (and Appendix IV) provide further information to enable the user, and potentially the patient, to make an informed decision that weighs the residual risk against the benefit of using the device.

15.4 Risks Associated with Participation in this Clinical Investigation

Protocol-required assessments are summarized in Section 6.7. Possible risks and discomforts associated with participation in the study will be similar to those associated with any routine dual-chamber pacemaker implantation procedure and related follow-up procedures.

Study-specific assessments that are not considered standard of care include femoral vein access instead of subclavian vein access, six-minute walk test and treadmill tests for rate response evaluation, in-clinic AV Synchrony assessments, 24-hour Holter monitoring, and EQ-5D quality of life assessment. A subject may experience fatigue, shortness of breath, chest pain and/or leg cramps during six minute walk and treadmill tests; this is mitigated by performing this test under the supervision of a trained professional and in a testing area where medical care is immediately available.

15.5 Steps Taken to Control or Mitigate Risks

In-depth recommendations, special precautions, and instructions regarding patient selection, vessel sizing, device handling, device placement and system removal are included in the IFU/IB.

Clinical Investigation Plan for Europe

The IFU/IB also states that the devices can only be used by physicians who have received appropriate training on how to use the device. This statement is interpreted to mean that the physician users are expected to be aware of the known and foreseeable safety risks associated with the use of the devices including the surgical and/or non-surgical treatment of these conditions.

Risks associated with the use of the device under investigation are minimized through device design, investigator selection and training, pre-specified patient eligibility requirements, study monitoring to ensure adherence to the protocol, and the use of a DSMB.

Sites will report all adverse events and device deficiencies to the Sponsor and the Sponsor will monitor internally for safety surveillance purposes.

15.6 Risk to Benefit Rationale

It is concluded from preclinical data (risk analysis and literature review) that clinical risks are comparable to those associated with currently available therapy (transvenous dual-chamber pacing). Uncertainty exists in relation to risks associated with novel features (percutaneous delivery via a femoral vein and the possibility dislodgement or migration). These residual risks cannot be estimated with confidence without data from a clinical investigation. Taking into account the nature of the possible harm that could arise from these device-related risks and the assurance provided by pre-clinical data, the risk-benefit balance associated with the use of the LP in a clinical trial is considered to be favorable.

Clinical Investigation Plan for Europe

16.0 APPENDICES

APPENDIX I: ABBREVIATIONS AND ACRONYMS

Abbreviation	Definition	Abbreviation	Definition
LP	Leadless Pacemaker	ICF	Informed Consent Form
DR	Dual-Chamber	EC	Ethics Committee
CIP	Clinical Investigational Plan	IFU	Instructions for Use
VR	Single-Chamber (Ventricular)	ICD	Implantable cardioverter defibrillator
i2i	Implant-to-implant	CRT	Cardiac resynchronization therapy
RA	Right Atrium	ICE	Intracardiac Echocardiography
RV	Right Ventricle	RRT	Recommended Replacement Time
ECG	Electrocardiogram	PG	Performance Goal
EGM	Electrogram	EDC	Electronic Data Capture
CFR	Complication Free Rate	CAEP	Chronotropic Assessment Exercise Protocol
CEC	Clinical Events Committee	6MWT	Six-Minute Walk Test
DSMB	Data Safety Monitoring Board	CRF	Case Report Form
SADE	Serious Adverse Device Effect	SAE	Serious Adverse Event
AV	Atrioventricular	UADE	Unanticipated Adverse Device Effect
AMS	Automatic Mode Switching	LCB	Lower Confidence Bound
IB	Investigator Brochure	HRS	Heart Rhythm Society
ESC	European Society of Cardiology	AHA	American Heart Association

Clinical Investigation Plan for Europe

APPENDIX II: DEFINITIONS

Adverse Event: An adverse event (AE) is any untoward medical occurrence, unintended disease or injury, or untoward clinical signs (including abnormal laboratory findings) in subjects, users or other persons, whether or not related to the medical device under investigation and whether anticipated or unanticipated.

Note 1: This definition includes events related to the medical device under investigation or the comparator.

Note 2: This definition includes events related to the procedures involved.

Note 3: For users or other persons, this definition is restricted to events related to medical devices under investigation.

The adverse event definition follows both ISO14155 Section 3.2 and MDCG 2020-10/1 guidance documents.

Attempted Implant: An implant procedure when the Aveir Introducer Sheath or Aveir dilator is inserted through the skin of the access site.

Complication: A device- or procedure-related serious adverse event, including any adverse event that prevents initial implantation.

Cardiac Tamponade: Confirmed or suspected accumulation of fluid in the pericardial space.

Cardiac Perforation: An excursion of the LP through the cardiac muscle. Signs and symptoms of a perforation by LP may include radiographic evidence of excursion of the LP into the pericardial sac, abnormal echocardiography indicative of a perforation, the accumulation of fluid in the pericardium, cardiac tamponade, or subject symptoms such as chest pain and discomfort.

De Novo: Subjects who do not have an implanted pacemaker on the date of consent through the date of the Aveir LP implant.

Device deficiency: Any inadequacy in the identity, quality, durability, reliability, usability, safety or performance of an investigational device, including malfunction, use errors or inadequacy in information supplied by the manufacturer including labelling.

Device-malfunction: the failure of a device to meet its performance specifications or otherwise perform as intended. Performance specifications include all claims made in the labeling for the device. The intended performance of a device refers to the intended use for which the device is labeled or marketed.

Diaphragmatic/Phrenic Nerve Stimulation: Electrical activation of the diaphragm muscle by the device output pulse. The abrupt diaphragmatic contraction is noted clinically as hiccups

Clinical Investigation Plan for Europe

associated with each pacing stimulus. The pacing stimulus may stimulate the diaphragm either directly or indirectly via the phrenic nerve.

Dislodgement: The LP separates from the endocardium after the implant procedure has been completed.

Elevated Pacing Thresholds (RV): Pacing thresholds > 2.5 V at 0.4 ms at implant. Following lead maturation at 6-8 weeks, an increase in pacing thresholds of 1.2 V at 0.4 ms or greater between visits. This definition is intended to serve as a guideline and it is understood that individual subjects may have unique situations.

Elevated Pacing Thresholds (RA): Atrial pacing thresholds > 4.0 V at 0.4ms on or after the pre-discharge assessment, or if there is an increase in atrial pacing thresholds of 1.2V at 0.4 ms or greater between visits. This definition is intended to serve as a guideline and it is understood that individual subjects may have unique situations.

Established i2i Communication: A situation at the end of an implant procedure where non-zero i2i throughput in either LP transmission direction (i.e. A2V or V2A) has been demonstrated. If any of the following situations occur, i2i communication will NOT be considered established:

- a) Implanter decides to retrieve 1 or 2 LPs and not replace them exclusively due to unacceptable i2i communication; OR
- b) Implanter deliberately programs the LPs to a non-dual chamber pacing mode due to unacceptable i2i communication; OR
- c) There is zero i2i throughput in both LP transmission directions (i.e. atrial LP to ventricular LP AND ventricular LP to atrial LP)

Intermittent or loss of i2i communication: When the subject either (a) has their Aveir DR system programmed to a non-dual chamber pacing mode at the end of any pre-discharge or follow-up visit solely due to unsatisfactory i2i communication even in the absence of untoward clinical signs, or (b) undergoes a system revision intervention due to unsatisfactory i2i communication.

Implant procedure duration: Defined as the time from delivery catheter and LP insertion to removal.

Implant success rate: Defined as the number of *de novo* subjects leaving the implant procedure with both implanted and functioning LP devices, divided by the number of subjects in whom implantation is attempted.

Inadequate Fixation: When an LP separates from the endocardium after being released from the Delivery Catheter during the implant procedure.

Loss of Capture: The inability of the device's output pulse to result in depolarization and contraction of the ventricle. Causes include insufficient stimulus strength, separation of the electrode from the myocardium and placement of the stimulating electrode in contact with a non-responsive portion of the myocardium such as scar tissue. Delivery of an output pulse at a time

Clinical Investigation Plan for Europe

when the myocardium is physiologically refractory is not loss of capture, since capture is not physiologically feasible.

Loss of Sensing: A condition in which the pulse generator is unable to sense intrinsic cardiac signals.

Migration: The movement of the LP to a different position outside the right ventricle and RVOT (for ventricular LP) or right atrium (for atrial LP).

Oversensing: The detection of inappropriate electrical signals by the pulse generator's sense amplifier. These signals, such as myopotentials, electromagnetic interference, or T waves must be of sufficient duration to interfere with normal device function.

Premature Deployment: When an LP completely separates from the Delivery Catheter before the LP was intended to be released by the implanter during the implant procedure

Procedure duration: Defined as the time from femoral introducer insertion to removal.

Serious Adverse Event (SAE): Any untoward medical occurrence that:

- a. Led to death,
- b. Led to serious deterioration in the health of the subject, that either resulted in
 1. A life-threatening illness or injury, or
 2. A permanent impairment of a body structure or a body function, or
 3. In-patient or prolonged hospitalization, or
 4. Medical or surgical intervention to prevent life-threatening illness or injury or permanent impairment to a body structure or a body function, or requires an invasive strategy to remedy
 5. Chronic disease
- c. Led to fetal distress, fetal death or a congenital abnormality or birth defect including physical or mental impairment.

NOTE: Planned hospitalization for a pre-existing condition, or a procedure required by the CIP, without serious deterioration in health, is not considered a serious adverse event.

Sponsor understands that the following items meet the definition of serious adverse event if they require hospitalization or prolong hospitalization, even though an invasive approach may not be necessary to resolve: AV fistula, pseudoaneurysm, blood transfusions, tricuspid valve damage, pericardial effusion, pulmonary embolus, device dislodgement, right ventricular or right atrial perforation, thrombus formation on the device, ventricular arrhythmias even if not associated with an invasive strategy to remedy.

Non-invasive means such as device re-programming do not meet the criteria for medical or surgical intervention.

Successful Implant: A subject who leaves an attempted *de novo* implant procedure with functioning atrial and ventricular LPs implanted, including established i2i communication

Clinical Investigation Plan for Europe

Successful Upgrade: A subject with a pre-existing Aveir ventricular LP who was successfully implanted with an Aveir atrial LP, and the Aveir VR LP can be programmed to a dual-chamber mode

Time to discharge: Defined as the time from introducer sheath removal to discharge.

Unanticipated (serious) adverse device effect (UADE/USADE): Any serious adverse effect on health or safety or any life-threatening problem or death caused by, or associated with, a device, if that effect, problem, or death was not previously identified in nature, severity, or degree of incidence in the investigational plan or application (including a supplementary plan or application), or any other unanticipated serious problem associated with a device that relates to the rights, safety, or welfare of subjects. [21 CFR 812.3(s)]

Unavoidable adverse event: An unavoidable AE is defined as an adverse event related to the implant procedure that is expected to occur for a projected duration in all subjects.

Undersensing: The failure of the pulse generator to sense R-waves, causing delivery of inappropriately timed, asynchronous or competitive output pulses. Undersensing can sometimes be corrected by programming the device to a more sensitive setting, i.e., decreasing the millivolt value.

Unsuccessful Implant: A subject who leaves an attempted *de novo* implant procedure without a functioning atrial or ventricular LP implanted, or where i2i communication was not established.

Unsuccessful Upgrade: A subject with a pre-existing Aveir ventricular LP who leaves an attempted upgrade procedure without an Aveir atrial LP or where the Aveir VR LP cannot be programmed into dual-chamber mode.

Upgrade success rate: Defined as the number subjects with pre-existing Aveir ventricular LPs leaving the upgrade procedure with an Aveir atrial LP and can be programmed in a dual-chamber mode, divided by the number of subjects in whom an upgrade is attempted.

Clinical Investigation Plan for Europe

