APPENDIX IV: FORESEEABLE ADVERSE EVENTS AND ANTICIPATED ADVERSE DEVICE EFFECTS

Access site bleeding event*	Interruption of desired LP function due to electrical interference, either electromyogenic or electromagnetic
Air embolism	Ischemic Stroke
Ateriovenous fistula	Loss of normal device function due to component malfunction
Cardiac arrhythmias	Nausea
Cardiac perforation	Oversensing
Cardiac tamponade	Pacemaker syndrome
Death	Palpitations
Device dislodgement	Pericardial effusion or rub
Dizziness	Pericarditis
Dyspnea	Peripheral nerve damage
Embolization of foreign material	Phrenic nerve/diaphragmatic/extra-cardiac stimulation
Embolism	Pneumothorax/Hemothorax
Endocarditis	Premature battery depletion
Excessive bleeding	Premature deployment with LP migration
Exit block	Premature deployment without LP migration
Failure to capture/loss of capture	Programmer/software anomaly
General surgery risks and complications from comorbidities such as hypotension, hypertension, groin pain, respiratory failure, pneumonia, cardiac failure, reaction to sedation, renal failure/kidney injury, anemia, and death	Pseudoaneurysm formation
Heart Failure	Pulmonary embolism
Helix Distortion	Reaction/Toxic Effect due to contrast media
Hematoma formation, including retroperitoneal hematoma/hemorrhage	RV pacing induced cardiomyopathy
High impedance	Syncope
Hypersensitivity reaction to device materials or substances	Threshold elevation
Inability to disengage snare from docking button	Thromboembolism

Clinical Investigation Plan for Europe

Inability to interrogate or program due to programmer or LP malfunction	Thrombosis
Inability to release and/or redock the LP	Transient ischemic attack
Inadequate Fixation during implant with LP migration	Tricuspid valve damage and/or regurgitation
Inadequate Fixation during implant without LP migration	Undersensing
Inappropriate rate sensor response	Vascular dissection
Infection, local at access site, or systemic	Vascular perforation
Intermittent capture	Vascular puncture
Intermittent or loss of i2i communication	Venous occlusion
Intermittent or loss of sensing	

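### Appendix II does not separate cardiac tamponade from pericardial effusion, and limits loss of capture and undersensing to the ventricle, so descriptive CEC event counts can be misclassified.

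*Protocol*

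**What the plan says.** Protocol section 10.9.4 has the CEC adjudicate pre-specified events "as defined in the CEC charter and according to definitions provided in this CIP". SAP section 3.2 then summarises the adjudicated events descriptively, as counts and percentages over all enrolled subjects.

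Three entries in protocol Appendix II matter here:

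- Tamponade: "Cardiac Tamponade: Confirmed or suspected accumulation of fluid in the pericardial space".
- Loss of capture: "The inability of the device's output pulse to result in depolarization and contraction of the ventricle".
- Undersensing: "Undersensing: The failure of the pulse generator to sense R-waves, causing delivery of inappropriately timed, asynchronous or competitive output pulses".

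Appendix IV lists cardiac tamponade and, as a separate item, "Pericardial effusion or rub". The serious adverse event entry in Appendix II names effusion, but not tamponade, among events that are serious if they lead to or prolong a hospital stay: "tricuspid valve damage, pericardial effusion, pulmonary embolus, device dislodgement, right ventricular or right atrial perforation". Pericardial effusion has no definition of its own.

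For the atrium, the 24-hour Holter report (protocol section 4.3.1, SAP section 3.6) asks for strips of atrial undersensing and loss of capture.

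**The concern.** A definition that binds an adjudication committee should let it separate the events that the same document lists separately. The tamponade entry does not: pericardial fluid, even if only suspected, meets it in full, and nothing further marks off an effusion.

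The other two entries leave out the chamber of most interest. Protocol section 1.1.2 states that ventricular sensing and pacing need not be evaluated again, and it rests the AAI(R) indication on the atrial LP. Read literally, a failure to capture the atrium is not a loss of capture, and a failure to sense P-waves is not undersensing.

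At stake is the safety description of a device system in its first human study. A reader will look for the tamponade count and for atrial failure modes. Event frequency can also feed oversight: section 3.3 gives a raised frequency of anticipated device effects as an example of grounds for a recommendation by the data and safety monitoring board.

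**Working it through.** No sample size, power or significance level in the plan depends on these definitions, so there is no stated figure to reproduce. The check is a comparison of texts, with a small illustration.

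**1. Tamponade against effusion.**

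- The Appendix II tamponade entry requires pericardial fluid, confirmed or suspected, and nothing else.
- Appendix IV lists tamponade and effusion as two items.
- The seriousness rule in Appendix II names effusion alone and makes it conditional on hospitalisation.
- The cardiac perforation entry, directly after the tamponade entry, gives fluid in the pericardium and tamponade as two distinct signs. Under the tamponade entry they are the same thing.

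Three places treat the two as different, and the one definition supplied merges them.

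**2. Atrial coverage.**

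- Loss of capture names the ventricle; undersensing names R-waves.
- The Holter report applies both terms to the atrium.
- Other Appendix II entries do cover the atrium: elevated pacing thresholds has separate right-atrial and right-ventricular versions, migration names both chambers, and loss of sensing is chamber-neutral.
- Loss of sensing describes a generator that cannot sense, and Appendix IV lists undersensing apart from it. It therefore covers complete atrial sensing failure, but not clearly partial P-wave undersensing.
- The right-atrial threshold entry is a voltage criterion, not failure to capture.

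The gap that remains is atrial loss of capture and partial P-wave undersensing.

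**3. Do the confirmatory endpoints move?**

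- Primary safety (sections 4.1.1 and 8.2.1) and secondary safety (sections 4.1.4 and 8.2.4) count serious events related to the device or procedure. Relatedness and seriousness decide; the event term does not.
- Seriousness has its own criteria (section 7.1.2 and Appendix II), and none makes an event serious because it is called tamponade.
- Effectiveness endpoint #1 (section 8.2.2, SAP section 2.3.2) uses measured threshold and P-wave amplitude.

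Relabelling alone leaves the tests against 76.5%, 82% and 80% unchanged.

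**4. Illustration, on assumed counts.** Take N = 300, the number of de novo subjects planned for the primary endpoints, and one true tamponade.

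True rate = 1/300 = 0.33%. Labelled rate = (1 + e)/300, where e is the number of effusions without tamponade.

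| e | Labelled rate | Ratio to true rate |
|---|---|---|
| 1 | 2/300 = 0.67% | 2 |
| 2 | 3/300 = 1.00% | 3 |
| 3 | 4/300 = 1.33% | 4 |
| 5 | 6/300 = 2.00% | 6 |

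The ratio is 1 + e whatever the denominator, so the SAP's use of all enrolled subjects does not change it.

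**The case against.** The strongest reply is that this is a drafting slip in a glossary with no bearing on any hypothesis test. Much of that stands.

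- **Safety endpoints.** A reader might infer that a minor effusion called tamponade would be treated as life-threatening and so enter the primary or secondary safety endpoint. The documents contain no such route: the event must still meet the seriousness criteria, whatever its name.
- **Atrial failures.** A reader might infer that these fall outside every named category. They do not. Loss of sensing and the right-atrial threshold entry cover part of the ground, and Appendix IV lists capture and sensing failures without a chamber limit. Atrial threshold and sensed amplitude are also scheduled at implant and at each follow-up visit.
- **Certainty.** A reader might conclude that the reported rates will be wrong. That is not shown. The CEC charter, case report forms and table mock-ups are not in the documents and may define or tabulate the terms further. Nor does any rule give an event only one term, so the effusion count need not be emptied.

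This does not remove the conflict. Section 10.9.4 makes the protocol definitions binding alongside the charter. Appendix IV lists terms but does not define them. The Holter analysis stops once 50 subjects contribute and is limited to those with at least 25% atrial pacing, so it cannot stand in for event classification across the study.

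**Conclusion.** The point holds as a defect of descriptive event classification. Three definitions that the CEC must apply conflict with other parts of the protocol. Applied literally, they can overstate tamponade and leave atrial loss of capture and partial P-wave undersensing without a matching defined term.

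The size is unknown: the documents give no tamponade, effusion or atrial failure rates, and the two- to six-fold range above follows only from the counts assumed. The conclusion also assumes that the charter does not already resolve the terms and that adjudicated events are tabulated by type.

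Both complication-free rates and effectiveness endpoint #1 are unaffected, as is the sample size. The correction is still worth making, because these counts describe the safety of a new intracardiac system and the change is cheap.

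**What to change.** - Reconcile the Appendix II tamponade entry with Appendix IV, the seriousness rule and the perforation entry. Give effusion and tamponade separate definitions that an adjudicator can tell apart. The clinical criterion that separates them is for the sponsor and the CEC to set.
- Extend loss of capture to the chamber in which the LP is implanted, and undersensing to P-waves for the atrial LP and R-waves for the ventricular LP.
- Report loss of capture and undersensing by chamber in the SAP section 3.2 summaries.
- Align the CEC charter, and apply the corrected terms to any events already adjudicated.

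The cost is wording changes in Appendix II, the charter and the event tables, plus minor relabelling. No new data, procedures or subjects are needed.
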